#### **9.4.4. Post-void Residual Urine Volume**

PVR urine volume is assessed by ultrasound or bladder scan after the participant has performed a voluntary void. If a participant is required to begin use of CIC post treatment, the PVR urine volume will be measured after the participant has attempted to void voluntarily and prior to a catheterization. If a participant is not able to spontaneously void despite trying, then this will be recorded on the CRF and the PVR will not be measured.

After randomization, should a PVR urine volume indicate a clinically meaningful elevation, the participant should be asked to void once again (allowing the participant sufficient time to void). The PVR urine volume will then be re-assessed. For participants who have a PVR urine volume measurement repeated, only the repeat value should be recorded in the eCRF. Guidance on how to manage an elevated PVR, observed at any routine study visit or additional follow-up visit is provided. In summary, posttreatment PVR urine volume is divided into 3 categories:

- i) < 200 mL
- ii) between  $\geq 200$  mL and < 350 mL
- iii)  $\geq 350$  mL

Protocol required action depends on the PVR category as does the need for further visits to evaluate the participant. The need for CIC is also dependent on the PVR as well as the participant symptoms. This guidance is to ensure participants are appropriately followed up and CIC is only initiated when required (while also ensuring any unnecessary intervention is limited). Further details are given below.

This guidance does not preclude further actions if the investigator deems it necessary.

- i) PVR < 200 mL

No protocol required action needs to be taken. Participant continues to be followed as per the schedule of visits and procedures.

- ii) PVR  $\geq 200$  mL and < 350 mL

If a PVR of  $\geq 200$  mL but < 350 mL is identified at any posttreatment visit, the investigator will assess the participant for any spontaneously reported associated symptoms (such as voiding difficulties or sensation of bladder fullness), with the resulting action to be as follows:

**BOTOX® (Botulinum Toxin Type A)  
Purified Neurotoxin Complex**

a) If a participant reports associated symptoms that in the opinion of the investigator requires CIC to be initiated, then CIC should be managed as detailed in the CIC section (Section 9.4.5).

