b) If a participant does not report any symptoms or if they report associated symptoms that, in the opinion of the investigator, do not require CIC then the following will occur:

- The participant will be seen for an additional follow-up visit 1 week later, at which time the PVR and any associated symptoms will be reassessed and central laboratory urine analysis and culture/sensitivity will be performed. At this reassessment visit:
  - if the PVR is increasing and is associated with symptoms, that in the investigator's opinion require CIC, then CIC should be initiated and managed as detailed below in the CIC section
  - if the PVR is  $\geq 350$  mL then CIC should be initiated and managed as detailed below in the CIC section
  - if the PVR is increasing but is not associated with symptoms or is associated with symptoms that in the opinion of the investigator do not require CIC, then the participant will be seen 1 week later to determine if CIC has become warranted and should be initiated based on PVR and/or any associated symptoms. At this additional reassessment visit:
    - a central laboratory urine analysis and culture/sensitivity will be collected
    - if in the investigator's judgment CIC should be initiated, then CIC should be managed as detailed below in the CIC section
    - if CIC is not initiated and PVR continues to increase, the investigator will determine whether additional follow-up visits should occur
  - If the PVR is decreasing or is unchanged then the participant will continue per the protocol schedule of visits and procedures.

iii)  $\text{PVR} \geq 350$  mL

If a PVR of  $\geq 350$  mL is identified at any posttreatment visit (regardless of symptoms) then CIC will be initiated as detailed in the CIC section.

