#### **9.4.5. Clean Intermittent Catheterization**

The following guidance should be used for the initiation of CIC in this study. Sterile, single use intermittent catheters should be used. Indwelling catheters should not be used in this study.

**BOTOX® (Botulinum Toxin Type A)  
Purified Neurotoxin Complex***Initiation of Clean Intermittent Catheterization*

As described above in the [PVR section](#), CIC should be initiated per protocol when one of the following criteria is fulfilled:

- PVR is  $\geq 350$  mL at any posttreatment visit, regardless of whether the participant reports associated symptoms
- PVR is  $\geq 200$  mL and  $< 350$  mL and the participant spontaneously reports associated symptoms (ie, voiding difficulties, sensation of bladder fullness) that in the opinion of the investigator requires CIC.

The following will occur when initiating CIC (for elevated PVR as described above):

1. CIC is implemented and the participant should be instructed to perform CIC using sterile, single-use catheters (which will be provided to the participant)
2. An adverse event of urinary retention is recorded
3. Central laboratory urine analysis and culture/sensitivity are performed as per routine requirements at each study visit
4. The participant will be seen for a follow-up visit 1 week later where the PVR, associated symptoms, central laboratory urine analysis and culture/sensitivity will be reassessed. The investigator will determine whether the participant can then be followed per protocol scheduled study visits or whether additional follow-up visits should occur.

Once CIC is initiated, the status of CIC use should be documented in the participant record at each visit (ie, use/nonuse).

*Cessation of Clean Intermittent Catheterization*

CIC should be discontinued when the following criteria are fulfilled:

- the participant does not have any associated symptoms which in the opinion of the investigator require CIC AND
- the PVR is  $< 350$  mL

The date of discontinuation of CIC should be documented. If the investigator deems that CIC should not be discontinued even though the above criteria are fulfilled, then this should be documented and the reason given. Upon discontinuing CIC the participant will be seen for a follow-up visit 1 week later where the PVR, associated symptoms, central laboratory urine

**BOTOX® (Botulinum Toxin Type A)  
Purified Neurotoxin Complex**

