15.0 DATA HANDLING CONVENTIONS

15.1 STATISTICAL ANALYSIS VISIT WINDOWS

Table 15.1-1 presents the target visit day assigned for efficacy and safety analyses and the corresponding range of treatment days (statistical analysis window) during which an actual visit may occur.

Table 15.1-1. Statistical Analysis Visit Windows

Visit Timepoint	Target Visit Day^a	Statistical Analysis Window
Screening/Baseline	NA	Days < Time of Study Treatment on Day 1
Day 1	Day 1	Day 1 from Time of Study Treatment to Midnight
Week 2	Day 15	Days [2, 29]
Week 6	Day 43	Days [30, 64]
Week 12	Day 85	≥ Day 65
End of Study ^b	Week 12 or Study Exit Visit	

a Relative to the date of the first dose of study treatment. Day 1 = the date of study treatment. There is no Day 0 or Week 0.

[figure not shown]
b Presented in analysis tables for safety parameters, including but not limited to clinical laboratory values, and vital signs. If a participant completes the study, the Week 12 visit is the end of study visit. If a participant discontinues the study prematurely, their last study visit (study exit visit) is the end of study visit.

If the assessment date (if the assessment date is unavailable, use visit date instead) is on or after the date of the first dose of study treatment, the study day is calculated by assessment date – date of the first dose of study treatment + 1. If the assessment date is before the date of the first dose of study treatment, the study day is calculated by assessment date – date of the first dose of study treatment. Therefore, a negative day indicates a day before the start of the study treatment. There is no Day 0; day of randomization and study treatment is Day 1.

If a participant has 2 or more visits within the same statistical analysis window, the last visit with a non-missing value will be used for analysis purposes for that corresponding visit timepoint. All postbaseline assessments will be considered for PCS categorization. All assessments will be included in respective listings.

15.2

DIARY DATA CONVENTIONS

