15.0 DATA HANDLING CONVENTIONS

15.1 STATISTICAL ANALYSIS VISIT WINDOWS

Table 15.1-1 presents the visits assigned for efficacy and safety analyses and the corresponding range of treatment days (window) during which an actual visit may occur.

Table 15.1-1. Statistical Analysis Visit Windows

Derived Visit	Scheduled Visit Day^a	Window
Baseline	Day 1	Days \leq 1
Week 2	Day 15	Days [2, 29]
Week 6	Day 43	Days [30, 64]
Week 12	Day 85	Days [65, 99]
Week 16	Day 113	Days [100, 127]
Week 20	Day 141	Days [128, 155]
Week 24	Day 169	Days \geq 156
End of study ^b	Week 24 or Study Exit Visit	

a Relative to the date of the study treatment. Day 1 = the date of the study treatment.

b Presented in analysis tables for safety parameters, including but not limited to electrocardiograms, clinical laboratory values, and vital signs. If a participant completes the study, the Week 24 visit is the end of study visit. If a participant discontinues the study prematurely, their last study visit (study exit visit) is the end of study visit.

If the assessment date (if the assessment date is unavailable, use visit date instead) is on or after the date of the of study treatment, the study day is calculated by assessment date – date of the of study treatment + 1. If the assessment date is before the date of the study treatment, the study day is calculated by assessment date – date of the study treatment. Therefore, a negative day indicates a day before the start of the study treatment. There is no Day 0; day of randomization and study treatment is Day 1.

[figure not shown]
If a participant has 2 or more visits within the same window, the last visit with a nonmissing value will be used for analysis. All postbaseline assessments will be considered for PCS categorization. All assessments will be included in respective listings.

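### Minor: the last-visit-in-window rule lets the protocol's 1-week PVR recheck replace a raised scheduled PVR in the by-visit tables

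*SAP*

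**What the plan says.** **Windows.** Section 15.1 of each SAP assigns visits to day windows for efficacy and safety analyses alike. The Stage 2 tie-break is: "If a participant has 2 or more visits within the same window, the last visit with a nonmissing value will be used for analysis". In Stage 1, "the last visit with a non-missing value will be used for analysis purposes for that corresponding visit timepoint". The one exception is "All postbaseline assessments will be considered for PCS categorization". The criteria for potentially clinically significant (PCS) values are in Tables 11.2-1 (laboratory) and 11.3-1 (vital signs).

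**PVR outputs.** Section 11.4.2 of each SAP plans descriptives and changes by visit and at end of study. It also plans four PVR categories (cut at 100, 200 and 350 mL) for each postbaseline visit and for the entire study.

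**Follow-up of a PVR result (Protocol 9.4.4 and 9.4.5).**
- Below 200 mL: "No protocol required action needs to be taken. Participant continues to be followed as per the schedule of visits and procedures".
- 200 to below 350 mL without clean intermittent catheterization (CIC): "The participant will be seen for an additional follow-up visit 1 week later, at which time the PVR" is reassessed.
- After CIC is started, which the protocol requires at 350 mL or more: "The participant will be seen for a follow-up visit 1 week later where the PVR, associated symptoms" and urine tests are reassessed.
- More visits are allowed: "This guidance does not preclude further actions if the investigator deems it necessary".
- Where someone "is not able to spontaneously void despite trying, then this will be recorded on the CRF and the PVR will not be measured".

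**The concern.** The protocol creates the second visit because the first result was high, and the SAP then lets the second visit stand for the first. Whether a scheduled PVR survives into the by-visit table therefore depends on its own value. A low scheduled value has no mandated successor, whereas a high one usually does.

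At stake is a by-arm display of bladder emptying in a study meant to choose a dose. Protocol 3.2.4 reports that the PVR rise with injected drug was transient and peaked by Week 2. A last-in-window rule can hide a short rise of that kind.

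**Working it through.** The plan states no figure on this point, so there is none to reproduce. The check is date arithmetic followed by logic.

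**1. Does the recheck fall in the same window?** The inputs are the target days and windows of Stage 2 SAP Table 15.1-1, with recheck day = target day + 7. The last column is window end − 7 − target day.

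| Visit | Target day | Window | Recheck day | Inside? | Days late the scheduled visit can be |
|---|---|---|---|---|---|
| Week 2 | 15 | 2–29 | 22 | yes | 7 |
| Week 6 | 43 | 30–64 | 50 | yes | 14 |
| Week 12 | 85 | 65–99 | 92 | yes | 7 |
| Week 16 | 113 | 100–127 | 120 | yes | 7 |
| Week 20 | 141 | 128–155 | 148 | yes | 7 |

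The Stage 1 windows for Weeks 2 and 6 are identical. The last visit of each stage (Week 12 in Stage 1, Week 24 in Stage 2) is left out. Its window is open-ended, but it is the exit visit, and the documents as seen do not show whether a recheck follows it.

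**2. What is tabulated?** Take 280 mL on Day 15 and 150 mL on Day 22. Both days lie in 2–29, the later value is nonmissing, and Week 2 is shown as 150 mL, in the category from 100 to below 200 mL.

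**3. Which way can the table move?**
- *Participants with a scheduled PVR of 200 mL or more.* All start in the count at 200 mL or more. A recheck below 200 mL removes one; a recheck at or above 200 mL, or none measured, leaves it. The count can only hold or fall.
- *The whole arm.* Some later values can add to the count: a visit after CIC stops, a measured value after a scheduled PVR that could not be measured, or an extra visit at the investigator's discretion. The overall proportion therefore has no fixed direction.
- *The mean and the share at 350 mL or more.* A pair of 280 then 360 mL moves both up; 360 then 150 mL moves both down.

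**4. Does another rule prevent it?** The all-assessments exception is limited to PCS categorization, and PVR is in neither PCS table. Section 15.4 of each SAP deals with unscheduled postbaseline visits only for the end-of-study value, where it again takes the last one, and for PCS determinations. Neither rule keeps rechecks out of the visit windows.

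**5. Scale, by assumption only.** Let p be the share of an arm with a scheduled PVR of 200 mL or more, c the share of rechecks completed, and f the share of those below 200 mL. The arm then loses 53 × p × c × f participants from the count. With c = 1:

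| p | f = 25% | f = 50% | f = 75% |
|---|---|---|---|
| 2% | 0.3 | 0.5 | 0.8 |
| 5% | 0.7 | 1.3 | 2.0 |
| 10% | 1.3 | 2.7 | 4.0 |

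With c = 0.8 each entry is multiplied by 0.8. Upward replacements in a share u of the arm cancel the loss when u = p × c × f. No value of p, c, f or u comes from the documents.

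**The case against.** The case for leaving the text alone is that little is lost.

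- Every start of CIC triggers a urinary retention adverse event, tabulated by arm, and catheterization use is summarized.
- A raised PVR judged clinically significant without CIC is an adverse event in its own right (Protocol 9.2.6), and every assessment is listed.
- p may be small. The instillation pilot recorded no significant PVR increase (Protocol 3.2.4), and Protocol 5.5 expects that penetration may be lower than with injection.
- Protocol 9.4.4 has a clinically meaningful elevation re-measured after another void at the same visit, with only the repeat recorded. A recorded high value may therefore already be a confirmed one, which would make f smaller.
- Scheduled-value against last-value is partly a matter of convention.

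All of this stands and limits the weight. It does not remove the dependence of replacement on the result.

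A reader might also infer that the entire-study category is an undefined output and a defect in itself. The documents do not support that. Section 11.4.2 names end of study and entire study separately, so the last value is an unlikely meaning. The once-per-category counting in Protocol Table 10-3 leans towards any occurrence, and the table specifications are in a separate document that is not available here. What remains open is detail: windowed or all assessments, and maximum or any occurrence.

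**Conclusion.** The point holds and is minor. As written, a measured 1-week recheck replaces the raised scheduled PVR in the by-visit descriptives and categories of both SAPs. The effect is confined to descriptive tables, and no test depends on them. The cases least visible elsewhere are values from 200 to below 350 mL without CIC that are not reported as an adverse event.

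A reader might infer that the rule systematically understates PVR or conceals retention in the higher-dose arms. The documents do not support that. Only the count among participants with a raised scheduled value has a fixed direction, retention is captured separately, and no by-visit PVR rate is given from which to derive a bias by arm.

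The conclusion assumes visits near their target days (within the margins shown) and PVR measured at the visits listed. The schedule of activities is not shown, so the latter cannot be confirmed.

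**What to change.** In both SAPs:

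1. For by-visit PVR descriptives and categories, use the value from the scheduled visit, or the value nearest the target day if there is none.
2. As a companion, state in Section 11.4.2 that the entire-study category is the highest postbaseline PVR over all assessments, additional visits included.

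Leave the end-of-study value under Section 15.4 as it is. No clinical follow-up rule changes.

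The cost is SAP wording and a little table programming, with no new data. The drawback is that a rise seen only at a recheck leaves the by-visit rows. The second change is there to keep such rises: with 280 mL on Day 15 and 360 mL on Day 22, Week 2 would show 280 mL and the entire-study category would be 350 mL or more.

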15.2 DIARY DATA CONVENTIONS

CONFIDENTIAL

BOTOX® (Botulinum Toxin Type A)
Purified Neurotoxin Complex

Page 31

15.3 DERIVED VARIABLES

The following criterion will be used to determine the category of urinary episode for each entry in a participant's bladder diary.

1. A participant has a **micturition episode** if the participant response is yes to either one of the following question in the bladder diary:
 - Did you urinate into the toilet or collection container?
 - Did you use a catheter to urinate?
2. A participant has a **urinary incontinence episode (UIE)** if the participant response is yes to the following question in the bladder diary:
 - Did you have accidental urinary leakage?
3. A participant has a **urinary urgency incontinence episode (UIIE)** if the participant response is yes to both of the following two questions for one episode in the bladder diary:
 - Did you have accidental urinary leakage?
 - Was this episode associated with a sudden and urgent need to urinate?
4. A participant has a **urinary urgency episode (UUE)** if the participant response is yes to the following question in the bladder diary:
 - Was this episode associated with a sudden and urgent need to urinate?
5. A participant has a **nocturia episode** if the participant response is yes to the following question in the bladder diary:
 - Did this episode wake you from night sleep?

[figure not shown]
6. A participant has a **catheterization episode** if the participant response is yes to the following question in the bladder diary:

- Did you use a catheter to urinate?

The number of UIEs per day will be recorded in the participant bladder diary over 3 consecutive days at any time during the screening period for the screening diary, and over 3 consecutive days during the week prior to each post baseline visit. The average number of UIEs per day will be calculated as the total number of episodes recorded in the 3-day bladder diary divided by the total number of valid diary days (see [Section 15.2](#)). The average number of micturition episodes, UUIEs, UUEs, and nocturia episodes will be derived in a similar manner.

To determine stratification groups (≤ 9 or > 9 UUIEs/day) for participants during randomization, the concept of valid diary days was not used by investigators to calculate the average number of UUIEs per day. Instead, all UUIEs recorded on the bladder diary from the beginning to the end of the first 3 consecutive 24 hour periods during the screening period was used irrespective of whether it was a valid dairy day or not. After database lock, this calculation will be repeated see if the values obtained by Allergan (i.e. actual stratification group) is the same as that recorded by investigators in the IVRS (planned stratification group). Note that this is done only to check for mis-stratifications. All other analyses or derivations using bladder diary data will be based on valid diary days.

The average volume voided per micturition will be calculated using the bladder diary records within the 24-hour period where participants were required to collect and record the urine volume from each urinary episode. To obtain this value, the total volume voided will be calculated as the sum of the volume voided from the bladder diary records where urine volume was collected within this 24-hour period. The total volume voided will then be divided by the number of bladder diary records that were included in the sum.

CONFIDENTIAL

BOTOX® (Botulinum Toxin Type A)
Purified Neurotoxin Complex

Page 34

15.4 REPEATED OR UNSCHEDULED ASSESSMENTS OF SAFETY PARAMETERS

If a participant has repeated assessments before the start of the study treatment, the results from the final nonmissing assessment made prior to the start of the study treatment will be used as baseline. If end-of-study assessments are repeated or if unscheduled visits occur, the last nonmissing postbaseline assessment will be used as the end-of-study assessment for generating summary statistics. However, all postbaseline assessments will be used for PCS value determinations, and all assessments will be presented in the data listings.

15.5 MISSING SEVERITY ASSESSMENT FOR ADVERSE EVENTS

If severity is missing for an AE that started before the date of the dose of study treatment, an intensity of mild will be assigned. If severity is missing for an AE that started on or after the date of the dose of study treatment, an intensity of severe will be assigned. The imputed values for severity assessment will be used for the incidence summary; the values will be shown as missing in the data listings.

15.6 MISSING CAUSAL RELATIONSHIP TO STUDY DRUG FOR ADVERSE EVENTS

If the causal relationship to the study treatment is missing for an AE that started on or after the date of the dose of study treatment, a causality of yes will be assigned. The imputed values for causal relationship to study treatment will be used for the incidence summary; the values will be shown as missing in the data listings.

15.7 MISSING DATE INFORMATION FOR ADVERSE EVENTS

The following imputation rules only apply to cases in which the start date for AEs is incomplete (ie, partly missing).

Missing month and day

- If the year of the incomplete start date is the same as the year of the dose of study treatment, the month and day of the dose of study treatment will be assigned to the missing fields
- If the year of the incomplete start date is before the year of the dose of study treatment, *December 31* will be assigned to the missing fields
- If the year of the incomplete start date is after the year of the dose of study treatment, *January 1* will be assigned to the missing fields

Missing month only

- If only the month is missing, the day will be treated as missing and both the month and the day will be replaced according to the above procedure

Missing day only

- If the month and year of the incomplete start date are the same as the month and year of the dose of study treatment, the day of the dose of study treatment will be assigned to the missing day
- If either the year of the incomplete start date is before the year of the date of the dose of study treatment or if both years are the same but the month of the incomplete start date is before the month of the date of the dose of study treatment, the last day of the month will be assigned to the missing day
- If either the year of the incomplete start date is after the year of the date of the dose of study treatment or if both years are the same but the month of the incomplete start date is after the month of the date of the dose of study treatment, the first day of the month will be assigned to the missing day

If the stop date is complete and the imputed start date as above is after the stop date, the start date will be imputed by the stop date.

If the start date is completely missing and the stop date is complete, the following algorithm will be used to impute the start date:

- If the stop date is after the date of the dose of study treatment, the date of the dose of study treatment will be assigned to the missing start date
- If the stop date is before the date of the dose of study treatment, the stop date will be assigned to the missing start date

